1.4 ELECTROPORATION TO AMPLIFY THE RESPONSE TO NAKED DNA VACCINATION

Electroporation (EP) is the delivery of electrical pulses to destabilize the cell membrane and make it permeable for macromolecules such as DNA. Electroporation has been used to introduce DNA into different cell types in vitro, and has recently also shown success in in vivo applications. Gene transfer by EP has been obtained in skin (55), corneal endothelium (56), tumours (57-59), brain (60), liver (61, 62) and muscle (63, 64) of experimental animals. Electroporation is used in clinical treatments of tumours to enhance uptake of water soluble cytostatica (65).

DNA immunization has shown to be potent in small animals but on its own may be less efficient in larger animals. A limiting factor is the uptake of DNA. Low levels of uptake will result in low expression levels and the antigen may then be expressed at levels below the limit needed to induce an immune response. Electroporation enhances the antigen expression and the immune response is increased significantly. Small animal studies that show compared to naked DNA alone, DNA in combination with electroporation can be given at much reduced levels and still induce similar or better humoral and cellular immune responses.(66-68)

Electroporation is thought to enhance immunization in several ways. Antigen expression may be improved and the resulting high concentration of vaccine derived protein may be important for reaching a threshold for the immune response to the vaccine. Secondly transient and reversible muscle cell damage will occur; this damage is likely to have effects similar to those of adjuvant and will provide a "danger signal" that attracts antigen presenting cells (APC) to the site (69). It is also possible that other cell types beyond muscle cells may be transfected in the muscle tissue when electrical stimulation is used. (70)

An interesting effect of electroporation mediated DNA immunization is an IgG subclass shift. By electroporation the IgG2 and hence the cellular response is much more pronounced than without EP (Tollefsen et al., 2002). Ulmer reported enhanced cellular immune responses in non-human primates at the DNA vaccine meeting in Edinburgh 2002. Rath et al have shown that using gene gun, an efficient IgG1 response is obtained. However, using electroporation, both IgG1 and IgG2a responses were enhanced (66).

Figure 4: Humoral immune response following DNA vaccination with two different H. contortus Ag in

sheep. Ab titre in serum of each animal was determined and the group average was calculated. The line across the graph represents the average of the negative controls. DNA vaccination with EP is depicted as black symbols while the non-EP group is shown as white symbols. SEM are depicted for each point, The ratios represent the number of animals out of the total with titres above the control values for the EP group (top) and the non-EP group (bottom). The arrow represents DNA boosts with EP

In collaboration with Inovio AS, we have shown that electroporation based gene delivery results in a stronger immune response, both cellular and humoral, compared to plasmid injections without EP (37). While in our hands 50µg in 50µl of naked DNA appears to deliver the optimal immune response in mice, suboptimal concentrations and volumes could be injected while still retain a strong response if the EP was used. This may be a considerable advantage in larger animals and humans were it is impossible to scale up the dose and volume proportionally to the body mass.

It is possible that we will find that the immune response is weak in patients and we may have to explore heterologous methods of boosting this immune response. However our current murine data show that our vaccine can deliver a very strong and consistent CTL response when we use p.DOM as an immune alert signal in the construct. It appears likely that electroporation will improve the antigen delivery to muscle cells and to local APC and enhance the amount of antigen available for stimulation of an immune response. For this reason we feel that a trial with the proposed construct is warranted without further heterologous boosting strategies.

1.5 INVESTIGATIONAL PRODUCT

The analyses of the immune response to FrC-encoding DNA vaccines has revealed the promotion of antibody and CD4+ T cell responses. If the aim however is to induce cytotoxic T cells, the MHC I motifs encoded in FrC might compete with the target sequence for immunodominance. Removal of the second, C-terminal domain of FrC results in a DNA sequence, which is a potent stimulator for CTL responses against peptide sequences, linked 3' to the N terminal domain of FrC.(71)

We have so far used DNA vaccination to induce immunity against tumour derived idiotypic protein for patients with B-cell malignancies. These vaccines are patient specific and contain the tumour-derived immunoglobulin variable region genes, linked to an immune alert signal, which is the non-toxic fragment C (FrC) from tetanus toxin.

In vitro DNA idiotype vaccine against the tumour (35) unexpectedly but reproducibly protected animals against myeloma. The response was not antibody driven because there was no surface Ig on the tumour cells. Moreover, there is no candidate CTL motif in the scFv of the murine model myeloma, 5T33. It is likely that CD4+ T cells were the mediators of protection, suggesting that DNA vaccination favours the Th_1 response needed for protection.

The bacterial DNA which forms the plasmid backbone of the vaccine has potent adjuvant or immunostimulatory properties. These can be exploited to generate highly effective CTL and Th₁ responses.(72) These immunostimulatory effects are determined by the presence of specific unmethylated CG-containing sequences. DNA containing these sequences stimulates the innate immune system, leading to the production of IFN γ by NK cells and IFN α , IFN $\gamma\beta$, IL-12 and IL-18 by macrophages. The cytokine milieu created by the immunostimulatory sequences (ISS) biases the immune response to simultaneously delivered antigen, favouring the differentiation of naïve T helper cells to the Th₁ phenotype. Secretion of IFN γ by Th₁ cells favours the activation of CTLs.

Several studies are currently ongoing or have completed. They enrol patients with follicular lymphoma (LIFTT), multiple myeloma after autograft (MMIFTT), prostate cancer and CEA expressing malignancies. The latter two studies use vaccines with the p.DOM-epitope design.

All studies to date focus on immunological readouts. We find a reproducible and durable induction of immunity (cellular and humoral) against FrC and DOM in all studies. More importantly we find strong evidence for induction of immunity against the tumour associated antigens, both in the FrC based

vaccines (LIFTT and MIFFTT studies) and in the solid tumour studies using the p.DOM-epitope design. In the prostate study, strong and durable anti-epitope specific responses to the HLA A2 restricted epitope encoded in the vaccine were observed in over 2/3 of the patients analyzed to date. (73)

Based on our preclinical data using WT1 constructs (9) we now propose to test these in patients with haematological malignancies and using disease response as the primary endpoint.

1.5.1 STRUCTURE OF VACCINE

The vaccine is a circular plasmid DNA (pUMCV). The insert of DNA unique to the vaccine consists of p.DOM linked to the WT1 epitope sequence. The expression of the insert p.DOM-WT1 is regulated by a CMV promoter. The sequence of the DNA insert is:

pcUMCV – 4030 nucleotides italics: domain 1 (p.DOM) from Fragment C * WT1 epitope.

Two vaccines will be evaluated in this study: p.DOM-WT1-37 with the sequence: VLDFAPPGA (aa37-45) GTGCTGGACTTTGCGCCCCCGGGCGCT p.DOM-WT1-126 with the sequence : RMFPNAPYL (aa126-134) AGGATGTTTCCTAACGCGCCCTACCTG TAA is a stop codon for translation

1.5.2 MECHANISM OF ACTION OF VACCINE

The DNA vaccines are designed to induce protein expression of the p.DOM-WT1-37 and p.DOM-WT1-126 fusion proteins, respectively, in muscle cells and/or local antigen presenting cells.

Presentation of the protein by antigen presenting cells will stimulate anti p.DOM CD4 helper cells, which induce linked T cell help for the induction of CD8+ T cells against WT1-37 and WT1-126.

1.6 PRE-CLINICAL ANTI-TUMOUR ACTIVITY

Preclinical data from mice expressing the human HLA A2 molecule (HHD mice) have been obtained with the proposed DNA vaccine, encoding WT1 epitopes and p.DOM from FrC. We see strong induction of peptide specific CD8+ T cells which are able to kill peptide loaded T2 cells as well as human tumour cells, expressing WT1. No toxicity was observed in these animals after vaccination (9).

1.7 ANIMAL AND HUMAN TOXICOLOGY OF DNA VACCINATION

No adverse events have been observed in any of the animal cohorts studied with any of our DNA vaccine constructs. There is now a large body of data from human subjects, who have been vaccinated in our own clinical trials; the main side effects have been flu-like symptoms (WHO1) and tiredness (WHO1).

Other groups confirm the conclusions that DNA vaccination is safe in patients in a variety of clinical settings (74, 75).

In preparation for this clinical trial we examined, whether there could be bone marrow toxicity associated WT1 vaccination. In our preclinical model in HLA A2 transgenic mice we found no evidence for bone marrow toxicity. Colony formation from bone marrow cells was unchanged, even if high levels of WT1 specific T cells were induced in the animals (9).

1.8 ANIMAL AND HUMAN TOXICOLOGY OF ELECTROPORATION

Electroporation is a physical method which requires the delivery of energy in the form of electrical current to the target tissue. The current is delivered as defined pulses of controlled magnitude, polarity and duration. Too much current, too high current density or too long pulses can be harmful and cause permanent tissue damage. If however the right amount of current is delivered, a transient permeability change is induced in the cell membrane. The collaboration with Inovio allows us access to this group's considerable expertise in this field and we are therefore able to safely incorporate this strategy into our own DNA vaccination approach.

1.8.2 LARGE ANIMALS

A limited number of studies have been performed on larger animals in pigs.(76, 77) These studies were performed both with and without anaesthesia. The treatment was well tolerated without anaesthesia. Only limited muscle cell damage was seen, it is however difficult to find the exact same location of the electroporation since the treatment would influence about $1 \times 0.5 \times 1.5$ cm of the muscle mass per injection/electroporation.

1.8.3 HUMANS

Recently, a clinical trial was performed at Ullevål University Hospital, (Oslo, Norway) to investigate the toxicology and side effects of electroporation alone. 6 healthy volunteers were approached and consented after local ethical approval of the study had been obtained. Only saline was injected and up to 4 applications per volunteer were given over 30 minutes, each into a separate site in the thigh muscles. Pain was assessed by a graded questionnaire and with a visual analogue scale.

First, a pulse (20 ms) at 20 V was given, a second pulse was given at <70 V/<250 mA. Then six pulses of 20 ms were delivered within a period of 1.4 seconds. Delivery of 6 unipolar pulses led to strong contractions of the muscle as well to significant discomfort (CTC \leq 3) and moderate pain (CTC 2-3). The volunteers where then asked if they would accept a fourth pulse sequence of 6 pulses but now with a bipolar pattern (the polarity was switched during the pulse, 10 ms + 70 V/ 10 ms -70 V). 4/6 volunteers accepted the bipolar treatment. The bipolar treatment caused higher levels of pain and discomfort and may require sedation but quantitative differences was not assessable in this study. The treatment was very short (a total of 1.4 sec) only localized to the muscle and it was the conclusion of the patients that this method of vaccine delivery was tolerable. Acute pain and discomfort resolved immediately after application. The short term side effect was ache at the site of treatment which lasted for 2-3 days, much like pain after physical exercise. No skin reactions were observed. The first post treatment blood samples taken (full blood count, full biochemistry including CK and LDH) showed an increase of creatine kinase level 16-19 h

after the treatment. However, these levels were back to normal at next blood sampling (5 days after the treatment). By this time all subjective sensations related to the EP had resolved.

Our own dataset is now of 150 applications of EP to patients. In the study in prostate cancer no significant toxicity was detected in either biochemical, haematological or autoimmune parameters after delivery of DNA with EP (41). While painful, the pain and discomfort in our patients resolved within minutes of vaccination (41) and prophylactic or symptomatic administration of pain medication was not required (41).

1.9 RATIONALE FOR THE PROPOSED STUDY

The information of DNA vaccination in humans has closely resembled the murine data so far. DNA vaccination in humans appears to be safe (73, 78). The data from our own experience is now based on >80 patients in the mentioned studies. No vaccine related serious adverse events have been observed; the major side effects were ache at the site of injection, mild flu-like symptoms and tiredness.

In trials other than our own, DNA vaccines given to patients, including immunocompromised individuals have had only minor ill effects, comparable to what is seen with conventional vaccines. DNA vaccines against malaria have now been safely administered to normal volunteers (75, 78, 80). Monitoring of safety on this study will follow our previous protocols.

We plan to study the effect of DNA vaccination with two DNA vaccines, p.DOM-WT1-37 and p.DOM-WT1-126 in HLA A2+ patients with CML-CP and AML. Patients will be tested for HIV, HepB, C and Syphilis to protect the laboratory personnel and because these infections may have a significant impact on the immunocompetence of the patient.

2 TRIAL OBJECTIVES

The objectives are to evaluate:

- 1) Molecular response in patients with CML (BCR-ABL, WT1) and AML (WT1).
- 2) Time to disease progression, 2 year survival rate (patients with AML)
- 3) Correlation of molecular responses with immunological responses.

2.1 PRIMARY ENDPOINT

2.1.1 CML:

Molecular response of BCR-ABL (major or minor response or CMR, as defined in section 9.6).

2.1.2 AML:

Time to disease progression. Disease progression in AML is defined as disease relapse.

2.2 SECONDARY ENDPOINTS

2.2.1 CML:

- 1) Molecular response of BCR-ABL (major response or CMR, as defined in Section 9.6).
- 2) Molecular response of WT1 (major or minor response or CMR, as defined in Section 9.6).
- 3) Time to disease progression. Disease progression for CML patients is defined as a loss in complete haematological response, where at least one factor falls out of the following ranges (81):
 - WBC < 10×10^9 /L
 - Basophils < 5%
 - No myelocytes, promyelocytes, myeloblasts in the differential
 - Platelet count < 450 x 10^9 /L

- Spleen nonpalpable
- 4) Time to next treatment. A next treatment is defined as the first drug taken during the course of the study with an indication to treat CML.
- 5) Duration of molecular response:
 - a. Measured from the beginning of tyrosine kinase inhibitor treatment.
 - b. Measured from the time of obtaining informed consent
- 6) Overall survival.
- 7) Toxicity assessed according to NCI CTCAE v4.0.
- 8) Pain assessment immediately after vaccination
- 9) Pain assessment at 48 hrs post vaccination

2.2.2 AML:

- 1) 2 year overall survival
- 2) 2 year progression free survival.
- 3) Overall survival.
- 4) Molecular response of WT1 (major or minor response or CMR, as defined in section 9.6).
- 5) Toxicity assessed according to NCI CTCAE v4.0
- 6) Pain assessment immediately after vaccination
- 7) Pain assessment at 48 hrs post vaccination

2.2.3 HLA A2 positive patients only (CML and AML):

- 1) Immune response to WT1-epitope specific T cells in blood and/or bone marrow, using validated assays by ELISPOT and/or ICS and tetramer staining. A positive response using the validated assays by ELISPOT is defined in Section 9.6.
- 2) Number of WT1 specific T-cells after peptide challenge to the skin (wherever assessment is feasible).
- 3) Immune response to DOM, using validated assays by ELISA.
- 4) Immune response to DOM specific T cells, using validated assays by ELISPOT.
- 5) Number of humoral responses (B-cells) to the vaccine components, by ELISA.

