4 SELECTION AND WITHDRAWAL OF PATIENTS

4.1 INCLUSION CRITERIA

CML patients:

Philadelphia chromosome positive CML in chronic phase, in complete cytogenetic response (CCyR) but with detectable BCR-ABL transcripts and maintained the CCyR on tyrosine kinase inhibitor monotherapy for a minimum of 24 months

AML patients:

Patients with WT1+ AML complete remission (CR) post chemotherapy or AML in morphologic CR with incomplete blood count recovery (CRi) defined as patients who fulfil all of the criteria for CR except for residual neutropenia (<1,000/ μ L) or thrombocytopenia (<100,000/ μ L).

As the vast majority of AML express WT and evaluation in CR or CRi is technically not feasible, formal demonstration of WT1 expression in AML cells is not required. Where historical or relapsed samples become available, WT1 expression status will be evaluated post hoc.

All patients:

- ≥ 18 years of age,
- Written informed consent
- WHO Performance status of 0 or 1.
- For vaccination groups: HLA-A0201 positive in at least one allele
- For control groups: HLA A2 negative in both alleles
- Renal function and liver function (Creatinine <1.5 x upper limit of normal, liver function tests < 1.5 x upper limit of normal); Lymphocyte count 
> 1.0 x10⁹/l*; normal clotting
- HB>100 g/l
- Adequate venous access for repeated blood sampling according to protocol schedule.
- If sexually active and possibly fertile, patients must agree to use appropriate contraceptive methods during the trial and for six months afterwards.

* If the lymphocyte count is below 1.0 at the time of entry into the trial but has been over 1.0 in the last 6 months and has also not declined rapidly in the days and weeks preceding entry, then the patient is eligible.

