5.6 CONCURRENT MEDICATION AND REPLACEMENT

Systemic steroids or other drugs with a likely effect on immune competence are forbidden during the trial. The predictable need of their use will preclude the patient from trial entry. Inhaled steroids are allowed. Concomitant medication may be given as medically indicated.

Patients with CML-CP will continue on tyrosine kinase inhibitor therapy and the dose of tyrosine kinase inhibitor therapy will remain unchanged throughout the course of the study. Patients will continue on the same dose of tyrosine kinase inhibitor therapy as prior to enrolment. Details of the concomitant medication given must be recorded in the Case Report Form (CRF).

The patient must not receive other anti-cancer therapy or investigational drugs while on study.

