Given the funding envelope the study is begun under it is expected that the duration of the immunological evaluation of the study will extend beyond the evaluation of the primary endpoints and secondary endpoints. Immunological evaluation is also a rapidly changing field in which the tools are improved and newly developed quickly. To reflect this, in the consent form patients will be asked to permit this later use of material for additional immunological evaluations beyond the submission of the end of study report to the regulatory bodies.

9.6.1 MOLECULAR RESPONSE:

Definition of BCR-ABL Response

- For patients with a baseline BCR-ABL transcript level less than 11: CMR: 0 BCR-ABL transcript level with ABL control copy greater than or equal to 32,000; in TWO CONSECUTIVE tests. These patients cannot be assessed for a major or minor response as defined below.
- 2) For patients with a baseline BCR-ABL transcript level greater than or equal to 11:
 - a. CMR: 0 BCR-ABL transcript level with ABL control copy greater than or equal to 32,000; in TWO CONSECUTIVE tests.
 - b. Major response: a fall greater than 1 log in the BCR-ABL transcript level ratio.*
 - c. Minor response: a fall greater than 0.5 log in the BCR-ABL transcript level ratio.*

*Confirmed in an ABL control copy greater than or equal to 32,000 in two consecutive samples at any time during follow up.

Definition of WT1 Response

1) For patients with a baseline WT1/GUS ratio less than 0.1%:

CMR: 0% WT1/GUS ratio with GUS control copy greater than or equal to 32,000; in TWO CONSECUTIVE tests.

These patients cannot be assessed for a major or minor response as defined below.

- 2) For patients with a baseline WT1/GUS ratio greater than or equal to_0.1%:
 - a. CMR: 0% WT1/GUS ratio with GUS control copy greater than or equal to 32,000; in TWO CONSECUTIVE tests.
 - b. Major response: a fall greater than 1 log in the WT1/GUS ratio.*
 - c. Minor response: a fall greater than 0.5 log in the WT1/GUS ratio.*

*Confirmed in a GUS control copy greater than or equal to 32,000 in two consecutive samples at any time during follow up.

9.6.2 IMMUNOLOGICAL RESPONSE:

Definition of validated assay by ELISPOT response:

A positive response using the validated assays by ELISPOT will be determined by having all of the following criteria:

- More than 25 spots per million Peripheral Blood Mononuclear Cell (PBMC) assay;
- (increase in spot number exceeds spot number at baseline + 2 x standard deviation at baseline;

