10.2 ANALYSIS PLAN

Molecular Analysis

The analyses on molecular response will be performed on all patients with molecular data at a minimum of 2 post-baseline time points (HLA A2 positive patients must also have received at least 1 dose of the vaccine).

Immunological Analysis

To be evaluable for immunological response, positive HLA A2 patients must receive at least 1 dose of the vaccine and the immunological testing must be available until at least week 8 post first dose.

Safety Analysis

For safety analyses, all patients with positive HLA A2 status who received at least one study drug administration will be evaluable for toxicity. All controls will be included in the safety analyses, where relevant.

Other Analysis

For all other analyses, an intention to treat principle will be used.

10.2.1 ANALYSIS FOR CML PATIENTS ONLY:

Primary:

The primary endpoint is molecular response of BCR-ABL (major or minor response or CMR). For the purpose of analysis, response (as defined by section 9.6) will be measured at weeks 4, 8, 12, 16, 20, 32 and 11, 17 and 23 months. Fisher's exact test will be used to compare differences in proportions of molecular response in CML patients versus controls.

Secondary:

The primary analysis will be repeated for major response or CMR of BCR-ABL.

The analysis methods used for BCR-ABL will be repeated for WT1.

Progression free survival, duration of response and overall survival (as defined in Section 2.2) will be estimated using the method of Kaplan and Meier for each group. Survival estimates will be presented with 90% confidence intervals. These endpoints will also be compared between the CML patients and controls using log-rank tests.

Progression free survival for CML patients is defined in Section 2.2 and is measured as the time from date of consent to the study to date of progression or death from any cause. Alive patients who are progression free will be censored at their date of last follow up. Similar analysis will be performed for overall survival and duration of response.

Toxicity will be collected and evaluated according to the NCI CTC toxicity scale (v4.0) and compared between the vaccinated and control groups by Fisher's exact test.

10.2.2 ANALYSIS FOR AML PATIENTS ONLY:

Primary:

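### CML duration of molecular response is timed from TKI start or from consent, neither of which is the onset of an on-trial response, and is then compared by log-rank

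*Protocol*

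**What the plan says.** Section 2.2.1(5) of the protocol lists duration of molecular response as a CML secondary endpoint with two versions: (a) "Measured from the beginning of tyrosine kinase inhibitor treatment" and (b) "Measured from the time of obtaining informed consent". No version starts at the response.

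Section 10.2.1 adopts these definitions: "Progression free survival, duration of response and overall survival (as defined in Section 2.2) will be estimated" by Kaplan-Meier for each group, with a log-rank comparison against controls. It then defines progression-free survival from consent and says that duration of response is handled similarly.

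Three other places bear on when a response can begin:
- Section 9.6.1 defines major and minor BCR-ABL response as a fall of more than 1 or 0.5 log in patients classed by baseline level, with the condition "Confirmed in an ABL control copy greater than or equal to 32,000 in two consecutive samples at any time during follow up". CMR also needs two consecutive tests.
- Section 4.1 requires that patients have "maintained the CCyR on tyrosine kinase inhibitor monotherapy for a minimum of 24 months".
- Section 4.2 excludes anyone who has reached CMR at any time on TKI therapy.

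A neighbouring item, Section 2.2.1(4), reads: "A next treatment is defined as the first drug taken during the course of the study with an indication to treat CML". Section 5.6 says: "Patients with CML-CP will continue on tyrosine kinase inhibitor therapy".

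**The concern.** A duration of response should run from the moment the response exists to the moment it is lost. Both stated origins come before that moment. The time between origin and response is time in which loss of response is impossible, yet it is counted as response time. A late, brief response can then outscore an earlier and longer one.

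The comparison adds a second difficulty. Duration exists only in patients who respond, so a log-rank test compares subsets selected on an outcome observed after entry. The groups themselves are formed by HLA A2 genotype, and Section 3 calls the design non-randomised. Under (a), any difference between the groups in years on TKI before entry passes straight into the result. At stake is a secondary result that could be read as showing more or less durable vaccine responses when it partly reflects TKI history and time to response.

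**Working it through.** **The plan's own figure.** The only CML design figure is in Section 10.1.1: p0 = 5%, p1 = 20%, alpha = beta = 0.10, at least 4 responders in 32. An exact binomial search gives the same n = 32 and r = 4, with alpha 0.0738 and power 0.9069. Allowing for 10% drop-out, 32 / 0.90 = 35.6, rounded up to 36, as stated. These figures do not depend on the duration endpoint.

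**Can a response exist at either origin?** Major and minor responses are falls measured after baseline and confirmed in two consecutive samples during follow-up. CMR before entry is an exclusion. So a Section 9.6.1 BCR-ABL response begins after consent, and TKI start lies at least 24 months before that.

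**Size of the overstatement.** In months from consent (taken as the baseline visit, where the schedule places it), let R be the onset of response, L its loss, and T the time on TKI before consent, with T ≥ 24 from Section 4.1.
- Duration from onset: L − R
- Version (b): L, an excess of R
- Version (a): T + L, an excess of T + R, which is at least 24 + R

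Two illustrative patients, using scheduled visits (Section 9.5 has BCR-ABL measured at every visit):
- Patient A responds at months 11, 14 and 17 and no longer at months 20 and 23, so R = 11 and L = 20.
- Patient B responds at months 20 and 23 and no longer at months 24 and 27, so R = 20 and L = 24.

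| | From onset | Version (b) | Version (a) |
|---|---|---|---|
| A | 20 − 11 = 9 | 20 | at least 24 + 20 = 44 |
| B | 24 − 20 = 4 | 24 | at least 24 + 24 = 48 |

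A's response lasts 5 months longer, but version (b) ranks B ahead by 4 months. Under version (a) the order depends further on each patient's T.

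**How many patients contribute?** Expected vaccinated responders are 32 × 0.05 = 1.6 and 32 × 0.20 = 6.4, so about 2 to 6. The protocol fixes no size for the control group, so the number of control responders cannot be derived.

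**The case against.** The best defence is that Section 2.2.1(5), unlike items 1 and 2 of the same list, does not cite Section 9.6. That it means the on-trial response is an inference, and the point depends on it. The inference is reasonable, because the protocol defines no other molecular response. If a response to the TKI before entry were meant, TKI start would still not be its onset.

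A second defence is that so few responders make the result descriptive under any origin. That stands, and it argues for dropping the log-rank test rather than for keeping the origins. It is also fair that no upper limit can be put on the excess under (b): Section 10.2.1 lists assessments to month 23, Section 9.6.1 allows response at any time in follow-up, and Section 9 runs to 36 months.

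Two stronger readings of the same list are tempting, and the protocol does not support them.
- *Time to next treatment is zero for every CML patient, because all take a TKI from the first day.* The definition does fail to exclude that TKI. But the word next, the unchanged background TKI in Section 5.6, and the prospective collection of subsequent treatments in Section 9 show that a new treatment is meant. Section 10.2.1 names no analysis of this endpoint that would be corrupted. It is a wording defect.
- *Progression on a single blood count produces many false events and needs a repeat-count rule.* Section 2.2.1(3) says "where at least one factor falls out of the following ranges" and is silent on confirmation, but confirmation and dating rules are often left to the SAP. The protocol gives no rate of chance out-of-range counts, so any percentage would rest on an invented rate. Treating counts as independent would also clash with infection as the cause, since an infection can persist across visits. And evidence of disease progression ends vaccination under Section 4.4, so changing the definition is not purely statistical.

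**Conclusion.** The point holds for duration of response. As written, both versions measure something other than how long a response lasts. Version (b) is too long by the time from consent to response, and version (a) by at least 24 months more. The log-rank comparison rests on about 2 to 6 vaccinated responders and on groups that were not randomised.

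This assumes that Section 2.2.1(5) refers to the BCR-ABL response of Section 9.6.1; the responder count also assumes true rates between the design values. The 24 months comes directly from the eligibility rule. The effect is confined to a CML secondary endpoint: the primary endpoint, the sample size and the 4-of-32 rule stand.

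The next-treatment definition needs only a clarifying clause. On progression, no more is supported than asking that Sections 2.2.1(3) and 4.4 be reconciled.

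**What to change.** - **Section 2.2.1(5):** define duration in responders only, from the first of the two confirming samples to the first of two consecutive samples that no longer meet the Section 9.6 response threshold, or death, with censoring at the last sample. Name the transcript, cite Section 9.6, and say how a sample with fewer than 32,000 ABL control copies is treated.
- **Section 10.2.1:** report duration descriptively, by Kaplan-Meier for each group, and remove it from the log-rank comparisons. Time from consent to response can be reported separately.
- **Section 2.2.1(4):** state that the TKI being taken at consent does not count as the next treatment.
- **Sections 2.2.1(3) and 4.4:** ask the sponsor to state how the progression definition relates to its use as a reason to stop vaccination. No clinical rule is proposed here.

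The cost is an amendment to wording. BCR-ABL is already measured at every visit, so no new data are needed. The losses are a between-group p-value that so few responders could hardly support, and the censoring of a loss first seen at the last sample, where no later sample can confirm it.
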